# 1 Trial Registration

## 1.1 Data set

Data Category	Information
Primary registry and trial identifying number	ClinicalTrials.gov
Date of registration in primary registry	TBD
Secondary identifying numbers	TBD
Source(s) of monetary or material support	N/A
Primary sponsor	Royal Victoria Regional Health Centre Research Institute
Contact for public queries	[name] NP, MN [[contact]]
Contact for scientific queries	[name] [name] [[contact]] Royal Victoria Regional Health Centre Research Institute, Barrie, Canada
Public title	Monthly versus daily buprenorphine formulations for treatment of opioid use disorder (OUD)
Scientific title	A pragmatic, multi-centre, open-label, randomized, 12-month, parallel group, superiority study to compare the effectiveness of subcutaneous buprenorphine depot (Sublocade®) vs daily sublingual buprenorphine with naloxone (Suboxone®) for the treatment of opioid use disorder ( STOP IT )
Country of recruitment	Canada
Health condition/problem studied	Agonist treatment, opioid use disorder
Intervention	Experimental: Sublocade® Active Comparator: Suboxone®
Key Inclusion and exclusion criteria	
Ages eligible: 18 to 65 years  Sexes eligible: Male; Female; Other  OUD eligible: Moderate-to-severe OUD as defined by the Diagnostic and Statistical Manual of Mental Disorders – Fifth Edition (DSM-V)  Induction/Stabilization therapy: Started and stabilized on Suboxone® (8mg/2mg to 24mg/6mg) for ≥7 days as determined by the following criteria:
 
1) No allergic reaction to buprenorphine, and

	
2) Clinical Opiate Withdrawal Scale score <math>\leq 12</math> (scale:0-48), and
 
3) Opiate Craving Visual Analog Scale score <math>\leq 20</math> (scale:0-100)
 
Inclusion criteria:
 
1) Written informed consent prior to enrolment
 
2) Must have an active Ontario Health Insurance Plan number
 
3) Contact information (telephone) available
 
4) Must have drug insurance coverage for either medication for duration of study or demonstrate ability to pay for the drug out-of-pocket
 
Exclusion criteria:
 
1) Receiving any investigational drug for OUD in previous 4 weeks
 
2) Congenital long QT syndrome or QT prolongation at baseline

Study type	
Interventional
 
Allocation: randomized 1:1
 
Intervention model: parallel assignment
 
Masking: open-label
 
Primary purpose: comparative effectiveness

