#### 12.12 Healthcare utilization

Difference in incidence rates of healthcare days at 12-months from the date of randomization, where **healthcare days represent the number of days alive and registered for an emergency room visit or admitted to an acute care or mental health facility for opioid-related harms or poisonings**. For each group, the incidence rate is calculated by dividing the total number of healthcare days by the total person days exposure over the study period. The potential number of healthcare days for each patient is the number of days alive during the 12-month study period, with the maximum being 365 days. Any day in which a patient is documented to have had an emergency room visit or is admitted to an acute care or mental health facility for any opioid-related harm or poisoning will be counted as a healthcare day. To estimate the number of opioid-related harms and poisonings resulting in healthcare utilization, the Discharge Abstract Database, Ontario Mental Health Reporting System database, National Ambulatory Care Reporting database, Registered Persons Database, and Office of the Registrar General of Ontario database will be linked to each patient's Ontario Health Insurance Plan number and the following opioid-related harms and poisonings International Statistical Classification of Diseases and Related Health Problems, Tenth Revision, Canada (ICD-10-CA) codes will be used to estimate the number of healthcare days utilized during the study period: Y45, F11.0-F11.9, T40.0-T40.4, T40.6. All opioid-related harms and poisonings resulting in the utilization of a healthcare day regardless of intent (ICD-10-CA X42 (accidental), ICD-10-CA X62 (intentional), and ICD-10-CA Y12 (undetermined)) will be included in the final analysis. Only those healthcare days in which opioid use was considered to be influential to the ER visit or hospitalization will be included and are identified by the following ICD-10-CA codes: M (most responsible diagnosis), 1 (pre-admit comorbidity), 2 (post-admit comorbidity), W or X or Y (Service transfer diagnosis). In addition, Diagnostic and Statistical Manual of Mental Disorders, 5th Edition codes 304.00 and 305.50 will be used to capture healthcare days for opioid-related harms and poisonings.

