The choice of healthcare days as a primary outcome reflects the desire to choose a measure that is patient-centered, readily measured and analyzed, and reflects a patient's holistic state rather than a specific symptom or arbitrary measure of effectiveness of opioid substitution therapy on illicit opioid use. Healthcare days have many attractive properties: they are continuous, enhancing power; they can be analyzed reliably and flexibly, to account for different values patients may place on avoiding hospitalization; and in nearly all cases, they are unidirectional, in the sense that nearly all patients prefer longer lives to shorter ones, and to have more of those days spent outside a hospital than within. In addition, healthcare days as a measure of healthcare utilization facilitate the economic valuation of the differences in the two treatment regimens in the trial, an important issue considering the differences in costs and the non-inferior outcomes previously reported for measures of illicit opioid use. The approach used to measure healthcare utilization in this trial has been validated and is currently used by the Canadian Institute of Health Information to measure and report opioid-related harms, poisonings and deaths. This trial will utilize a measure of opioid-related harms and poisonings that is valid, objective, reproducible, relevant to both healthcare providers and patients with OUD, and should be responsive to treatment with both drugs used in this trial.

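### The healthcare-days rule in Section 12.12 can count a stay on the entry diagnosis alone, and no planned analysis shows how far the result depends on that

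*Combined protocol and SAP*

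**What the plan says.** Section 12.12 defines the second primary outcome as days alive and "registered for an emergency room visit or admitted to an acute care or mental health facility for opioid-related harms or poisonings". The counting unit is the day: any day on which a patient visits an emergency room or "is admitted to an acute care or mental health facility for any opioid-related harm or poisoning will be counted as a healthcare day".

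The qualifying ICD-10-CA codes are "Y45, F11.0-F11.9, T40.0-T40.4, T40.6". A restriction follows: "Only those healthcare days in which opioid use was considered to be influential to the ER visit or hospitalization will be included". The same sentence says how these days are recognised, namely by diagnosis type: "M (most responsible diagnosis), 1 (pre-admit comorbidity), 2 (post-admit comorbidity), W or X or Y (Service transfer diagnosis". The section then adds that DSM "codes 304.00 and 305.50 will be used to capture healthcare days for opioid-related harms and poisonings", with no statement of the position the code must hold.

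The entry criterion in Section 1.1 is "Moderate-to-severe OUD as defined by the Diagnostic and Statistical Manual of Mental Disorders", and Section 10.1 repeats it. Section 12.13 defends the method on the ground that it "has been validated and is currently used by the Canadian Institute of Health Information to measure and report opioid-related harms, poisonings and deaths".

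Section 20.11b plans one Poisson regression of the day counts with an indicator for OUD severity and any unbalanced baseline variables. It plans no analysis by diagnosis type and no adjudication of stays.

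**The concern.** The endpoint is meant to measure care for opioid harm. Its code list includes the whole F11 block and two DSM codes, and its type list accepts a comorbidity recorded before or after admission. In a general population, an OUD code on a record separates a few patients from the rest. Here everyone has the disorder and is being treated for it. If a coder records OUD as a type 1 or type 2 diagnosis during a stay for an injury or an infection, the rule counts every day of that stay.

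Two things are at stake. Days unaffected by treatment pull the rate ratio toward 1. And any difference that is found cannot be read as a difference in opioid-related harm unless one knows how much of the count comes from comorbidity-only stays. Section 14.1 rests its cost-offset argument on a 50% reduction in this endpoint, so both the size and the meaning of the ratio matter.

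**Working it through.** **Step 1: does the restriction add a filter?** Section 12.12 puts the intent (opioid use was influential) and the test (types M, 1, 2, W, X, Y) in one sentence, and the test is the only means given of applying the intent. A stay with F11 coded as type 1 and an unrelated most responsible diagnosis passes. The DSM codes carry no type or position test at all. The case report form records whether a visit was opioid-related, yes or no (Sections 18.11b and 18.12), but the endpoint does not use that item.

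**Step 2: the plan's own figure for these rates.** Section 14.4 states 99% power for 2 versus 1 healthcare days per 1000 patient days, with 3650 patient days per group and two-sided alpha of 0.05. Expected counts are 0.002 × 3650 = 7.3 and 0.001 × 3650 = 3.65. For two Poisson rates, power = Φ(|r1 − r2| / √((r1 + r2)/T) − 1.96).

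- T = 3650: Φ(0.001/0.000907 − 1.96) = Φ(−0.857) ≈ 20%. The 99% is not reproduced.
- T = 45 × 365 = 16 425, everyone followed for a year: Φ(0.001/0.000427 − 1.96) = Φ(0.380) ≈ 65%, with expected counts of about 33 and 16.

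This discrepancy is a separate matter and neither proves nor depends on the present point. It shows only that there is no spare power to absorb dilution. Treating days as independent also flatters these powers, because days come in stays.

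**Step 3: dilution with equal entry.** Assumptions: 2 versus 1 days per 1000 are opioid-caused, and b unrelated days per 1000 qualify in each arm. The documents supply neither the split nor b. Ratio = (1 + b)/(2 + b).

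| b per 1000 | Comparator | Depot | Ratio | Reduction seen | Power at 16 425 days |
|---|---|---|---|---|---|
| 0 | 2 | 1 | 0.50 | 50% | 65% |
| 1 | 3 | 2 | 0.67 | 33% | 44% |
| 2 | 4 | 3 | 0.75 | 25% | 33% |
| 4 | 6 | 5 | 0.83 | 17% | 23% |

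**Step 4: the other reading of the planning rate.** Section 14.3 and the footnote to Table 4 define the rate as hospital days plus emergency visits, without an opioid restriction. Suppose the 2 per 1000 is therefore the total, a share s of it is unrelated, and treatment halves only the rest. The depot rate is 2s + 2(1 − s) × 0.5 = 1 + s, so the reduction seen is 0.5 × (1 − s). For s = 0.10, 0.25, 0.50 and 0.75 it is 45%, 37.5%, 25% and 12.5%. The direction is the same on either reading; only the unknown quantity changes.

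**Step 5: weight of one stay.** Because every day counts, one unrelated stay of 7 days (assumed length) nearly equals the 7.3 comparator days expected on the plan's 3650-day basis. It is 7/32.85 = 21% of the comparator count expected with 45 patients followed for a year. For scale, Section 5.1.2 gives opioid-related stays a median of 3 days and a range of 1 to 207.

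**The case against.** The plan states its intent to exclude unrelated stays and treats the listed types as the markers of influence. Whether coders would give an incidental OUD history type 1, and whether F11 codes record the disorder as well as an acute harm, depends on coding standards that are not in the documents. This stands: the number of unrelated days that would enter is unknown, and it could be small. It does not remove the gap, because nothing in the printed rule excludes such a stay.

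The planning rates of 2 and 1 are not described as opioid-caused. This also stands, and Step 3 is therefore an illustration, not a consequence of the plan's rates.

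Breadth is partly deliberate. Section 12.13 wants a measure of the patient's whole state that supports economic valuation, and a narrow rule would lose stays to which opioid use contributed without being the main diagnosis. That is a sound reason not to replace the primary definition. The support drawn from national reporting is weaker, since the section does not discuss a cohort in which everyone has the diagnosis.

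A reader might infer a stronger charge: that daily dosing makes OUD more likely to be coded in the Suboxone arm, so that the rule would produce a false benefit for Sublocade. The documents do not support this. They describe neither inpatient dosing nor hospital coding by arm. Section 11.4 allows breakthrough Suboxone in the Sublocade arm. The open-label statement in Section 17 covers participants, clinic providers and study personnel, and does not mention hospital coders. Unequal coding remains possible, but no percentage of bias should be attached to it.

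**Conclusion.** The point holds as a gap between the stated intent and the operational rule. A comorbidity code for the condition that every participant must have is enough to count a whole stay, and no planned analysis would reveal how often that happened. With equal entry the effect is loss of contrast and power, not a false benefit. Under the assumed rates, a 50% reduction would show as 33%, 25% or 17% with 1, 2 or 4 unrelated days per 1000 in each arm. These figures rest on an assumed split, an assumed volume of unrelated stays, and the coding assumption that OUD itself can be recorded under F11 or the two DSM codes. A reader might also infer that the primary definition is invalid and must be replaced; the documents do not support that, because narrowing it has its own cost. This is a cheap improvement that bears on whether a difference may be called opioid-related.

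**What to change.** Keep the printed rule as primary. In Sections 12.12 and 20.11b, pre-specify a sensitivity analysis that counts a day only if one of these holds:

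- (a) T40.0–T40.4, T40.6 or Y45 is present in any listed type;
- (b) F11.x is the most responsible diagnosis or the main emergency room problem, or 304.00 or 305.50 is the principal diagnosis of a mental-health stay.

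Report both results side by side, and attribute a reduction to opioid-related harm only with the narrow result shown. Fix the wording before any outcome data are seen: Section 17 leaves the analysts unmasked, so a definition chosen later would carry little weight.

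Add all-cause healthcare days, which do not depend on opioid coding, if the ICES extract includes all stays. Section 12.12 describes retrieval by opioid codes, and the ICES letter says its quote may change with scope, so this part may cost more. The all-cause utilization recorded as serious adverse events (Section 22) is not a full substitute, because the clinics can see records from only one hospital and otherwise rely on self-report (footnote in Section 18.11b).

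The core change costs amendment wording and one more analysis of the same linked codes. Its drawback is that the narrow version has fewer events and wider intervals.

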#### 12.13 Rationale for primary outcome measures

While the measurement of opioid positivity during opioid substitution therapy is a consistent primary outcome measure used across most trials, there is no gold standard measure of treatment effectiveness. Even in the 3 trials reviewed in Table 1, each had a different measurement outcome for opioid positivity despite 2 of those trials being conducted by the same research group. In a systematic review of outcome measures used in opioid substitution treatment that included 60 trials, opioid positivity was the second most commonly reported outcome. In those trials measuring opioid positivity, there were 17 different definitions, including a further 8 variations in measurement. In those studies that measured opioid positivity using urine drug screening, it was common practice to impute opioid positivity for missing data, often times as a requirement for regulatory agencies for evidence of efficacy and

other times as a practical matter of OAT management in the clinics. The imputation methods differed across studies, with few studies ever explaining the rationale for their technique. Urine drug testing was almost always accompanied by self-reports of opioid use, and is recommended as a standard of practice in opiate substitution therapy. The most commonly used tool to measure self-reports of opiate use was the Timeline Followback method. In those studies utilizing both urine drug testing and self-report to measure opioid positivity, opioid positivity was defined as any positive result in either one or both tests. This trial will utilize this measure of opioid positivity because it is consistent with previous approaches (valid), objective, reproducible, relevant to both healthcare providers and patients with OUD, and has been previously demonstrated to be responsive to treatment with both drugs used in this trial.

The choice of healthcare days as a primary outcome reflects the desire to choose a measure that is patient-centered, readily measured and analyzed, and reflects a patient's holistic state rather than a specific symptom or arbitrary measure of effectiveness of opioid substitution therapy on illicit opioid use. Healthcare days have many attractive properties: they are continuous, enhancing power; they can be analyzed reliably and flexibly, to account for different values patients may place on avoiding hospitalization; and in nearly all cases, they are unidirectional, in the sense that nearly all patients prefer longer lives to shorter ones, and to have more of those days spent outside a hospital than within. In addition, healthcare days as a measure of healthcare utilization facilitate the economic valuation of the differences in the two treatment regimens in the trial, an important issue considering the differences in costs and the non-inferior outcomes previously reported for measures of illicit opioid use. The approach used to measure healthcare utilization in this trial has been validated and is currently used by the Canadian Institute of Health Information to measure and report opioid-related harms, poisonings and deaths. This trial will utilize a measure of opioid-related harms and poisonings that is valid, objective, reproducible, relevant to both healthcare providers and patients with OUD, and should be responsive to treatment with both drugs used in this trial.

## 12.2 Secondary outcome measures

### 12.21 Medication satisfaction

Difference in the Medication Satisfaction Questionnaire scores. The questionnaire is a single-item, global, patient-completed instrument that has been validated to measure treatment satisfaction, initially in patients receiving antipsychotic treatment for schizophrenia, but subsequently used in trials measuring satisfaction with opiate substitution treatment. The question will be read aloud by the RAAM clinic healthcare providers or study personnel to the patient. The question asks, "Overall, how satisfied are you with your current Suboxone®/Sublocade® medication?". The responses are on a 7-point Likert scale, ranging from 1=extremely dissatisfied to 7=extremely satisfied. This questionnaire is valid, reproducible, relevant to both healthcare providers and patients with OUD, and has been shown to be responsive to opiate substitution treatment in previous studies.

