### 7.2 Secondary

- 1) To compare the effect of Sublocade® versus Suboxone® on improving patient satisfaction
- 2) To compare the effect of Sublocade® versus Suboxone® on improving patient quality of life
- 3) To compare the effect of Sublocade® versus Suboxone® on clinic retention
- 4) To compare the effect of Sublocade® versus Suboxone® on patient mortality

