## 10.1 Inclusion criteria

Patients eligible for the trial must comply with all of the following at randomization:

1. Ages 18 to 65 years old
2. OAT indicated for moderate- to severe-[OUD](#)
3. Attend a RAAM clinic in the North Simcoe Muskoka Local Health Integrated Network for opiate substitution treatment
4. Successfully completed induction and stabilization OAT with [Suboxone](#)® tablet or film defined as receiving 8mg/2mg to 24mg/6mg of [Suboxone](#)® for  $\geq 7$  days with no evidence of allergic reaction to [Suboxone](#)®, [Clinical Opiate Withdrawal Scale](#) (COWS) score  $\leq 12$  (scale:0-48) for  $\geq 24$  hours, and [Opiate Craving Visual Analog Scale](#) (VAS) score  $\leq 20$  (scale:0-100) for  $\geq 24$  hours
5. Must have an active Ontario Health Insurance Plan number
6. Must have a telephone that can receive calls, text messages or emails
7. Must have drug insurance coverage for either medication for duration of study or demonstrate ability to pay for the drug out-of-pocket

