## 11.4 Modifications

For eligible patients randomly allocated to Sublocade®, missed doses can be administered up to 42 days after the last dose. For those with longer intervals between Sublocade® doses, it will be up to the discretion of the RAAM clinic healthcare providers whether repeated induction and stabilization with Suboxone® is required, and if Sublocade® treatment should be re-

initiated. At the discretion of the RAAM clinic healthcare providers, some participants may receive breakthrough doses of Suboxone® and/or an increased maintenance dose of Sublocade® of 300 mg per month instead of 100 mg per month as clinically indicated to prevent opioid cravings (VAS  $\geq$  21) or withdrawal (COWS  $\geq$  5) symptoms. In some cases, Sublocade® doses may need to be reduced or discontinued due to adverse effects.

For eligible patients randomly allocated to Suboxone®, at the discretion of the RAAM clinic healthcare providers, some participants may receive breakthrough doses of Suboxone® and/or increased maintenance doses of Suboxone® as clinically indicated to prevent opioid cravings (VAS  $\geq$  21) or withdrawal (COWS  $\geq$  5) symptoms. Daily dose of Suboxone® should not exceed 24 mg buprenorphine. In some cases, Suboxone® doses may need to be reduced or discontinued due to adverse effects.

For eligible patients with abnormal vital signs (a change from baseline measurements and any of the following: systolic blood pressure  $\leq$  90 mm Hg OR mean arterial blood pressure  $\leq$  55 mm Hg OR heart rate  $\geq$  130 beats per minute OR temperature  $\geq$  38.1°C OR  $\leq$  36°C OR respiratory rate  $\leq$  8 breaths per minute OR  $\geq$  30 breaths per minute or mental status (Glasgow coma scale  $\leq$ 14), RAAM healthcare personnel will investigate the causes for these abnormalities prior to consideration of buprenorphine dosing, and make all necessary arrangements for medical management of the patient.

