#### 18.12 Study-specific data

Data	Description	Data type
Medication Satisfaction Questionnaire	"How satisfied are you with your medication?"	Categorical: Range 1-7
WHOQOL-BREF	26-item questionnaire measuring quality of life in 4 domains: physical health;	Continuous: Each domain score standardized to scores 0 (worse) to 100 (best)

	psychological health; social; environment	
Hospitalization 	Any Royal Victoria Regional Health Centre emergency room visits, admissions to hospital or mental health or detoxification centre since previous clinic visit (Yes: No)	Categorical
Reason for visit/admission	Opioid-related (Yes: No)	Categorical
Serious adverse events 	Hospitalization (for any reason)	Categorical
Reason	Opioid-related (Yes: No)	Categorical

 Only hospitalization events associated with the Royal Victoria Regional Health Centre are accessible to the RAAM clinic healthcare providers as they clinics share the same electronic health record system as previously described. All other hospitalizations would have to be self-reported by the participants and consent for access to the health records would then need to be secured by the RAAM clinic healthcare providers.

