## 20 Statistical methods

### 20.1 Outcomes

The intervention arm (Sublocade®) will be compared against the active comparator (Suboxone®) for all primary and secondary analyses. All analyses will be done according to original patient allocation regardless of whether they received the randomized treatment or were compliant with the study protocol (Intention-to-treat). All analyses will be conducted using STATA/MP 17.0 for Mac.

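### The Medication Satisfaction Questionnaire has no week 0 score, so the satisfaction model gives up a cheap baseline covariate

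*Combined protocol and SAP*

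**What the plan says.** - **Outcome.** Section 12.21 defines the outcome as "Difference in the Medication Satisfaction Questionnaire" scores between the arms. The item, "Overall, how satisfied are you with your current Suboxone®/Sublocade® medication", is read aloud and answered from 1 to 7. Section 1.1 lists it among the key secondary outcomes.
- **Objective.** Section 7.2 reads "To compare the effect of Sublocade® versus Suboxone® on improving patient satisfaction".
- **Schedule.** In the section 13 timeline, the MSQ row is marked at weeks 6, 12, 18, 24, 30, 36, 42 and 48, and is blank at weeks -1 and 0. The WHOQOL-BREF row starts at week 0.
- **Treatment before randomization.** Section 10.1 requires that participants have "Successfully completed induction and stabilization OAT with" Suboxone, with at least 7 days on it.
- **Analysis.** Section 20.12 fits a three-level linear mixed model with visit, a visit-by-treatment interaction and any baseline variables found to be unbalanced. It has no baseline MSQ term. Section 20.1 analyses by original allocation.

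**The concern.** The other repeated questionnaire in the same model section, the WHOQOL-BREF, has a week 0 value; the MSQ does not. The usual reason for omitting a baseline satisfaction score is that patients have not yet had a drug to rate. That reason does not apply here, because the stabilization requirement puts everyone on Suboxone before randomization.

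Without the baseline, stable differences between people in how they rate medication stay in the error of the treatment comparison. The trial has 45 participants per arm, a number set for the primary outcomes with no power statement for the MSQ, so precision on this outcome is limited from the start. A report also cannot say where satisfaction stood before the Sublocade arm changed drug. A baseline cannot be recovered once a participant has been randomized.

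**Working it through.** The plan states no sample size, power, SD or correlation for the MSQ, so there is no stated figure to reproduce.

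**Schedule.** Aligning the MSQ row of the section 13 table with its week header gives the eight visits listed above and nothing at week 0. The table was extracted from a PDF: the last WHOQOL-BREF mark falls two cells beyond the final header column. The MSQ marks, however, are evenly spaced six weeks apart and end at week 48, and the first WHOQOL-BREF mark falls at week 0.

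**Inputs**
- n = 45 per arm (section 14.4).
- Two-sided alpha 0.05, z = 1.960; 80% power, z = 0.842. These are conventional values, as used in section 14 for the primary outcome.
- r, the correlation between the week 0 and follow-up scores: assumed 0.3 to 0.5, with 0.7 as an optimistic value.
- One score per participant and no missing data. The planned model uses up to eight scores, so its exact figures would differ.

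**Variance.** Adjusting for a baseline multiplies the variance of the arm difference at a visit by 1 − r².
- r = 0.3: the reduction is 0.3² = 0.09, or 9%.
- r = 0.5: the reduction is 0.5² = 0.25, or 25%.

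**Detectable difference, in SD units**
- No baseline: (1.960 + 0.842) × √(2/45) = 2.802 × 0.2108 = 0.59.
- With a baseline, multiply by √(1 − r²):

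| r | √(1 − r²) | Detectable at 80% power |
|---|---|---|
| none | 1 | 0.59 SD |
| 0.3 | 0.954 | 0.56 SD |
| 0.5 | 0.866 | 0.51 SD |
| 0.7 | 0.714 | 0.42 SD |

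**Equivalent sample size.** The gain matches an unadjusted trial with n/(1 − r²) per arm: 45/0.91 = 49.5 at r = 0.3 and 45/0.75 = 60 at r = 0.5.

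**The case against.** The strongest defence is that nothing here is invalid. The outcome is a difference between randomized arms, and scores after randomization estimate it without a baseline. The MSQ is a secondary outcome with no sample-size basis, the gain rests on an assumed correlation, and the baseline would rate Suboxone even in the arm that then moves to Sublocade. All of this stands. It limits the point to a gain in precision. It does not remove the point, because the question is nearly free.

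Three stronger readings are tempting, and the documents do not support them.

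- **That patients who stop treatment leave the outcome**, because the item asks about the current drug. Section 18.22 does not treat protocol deviations as withdrawal, and it seeks consent to continue study-specific assessments, such as the WHOQOL-BREF, after withdrawal; section 18.12 lists the MSQ as study-specific data. The plan does not say what a patient on neither drug should rate, but that silence is not a rule excluding them. A bias estimate would need an assumed score gap and an assumed difference in stopping between arms. With equal stopping the bias is zero. The 20% and 50% in section 14.3 are loss to follow-up for another outcome, not differential stopping.
- **That switchers are analysed wrongly**, for example a Sublocade patient re-induced on Suboxone after a lapse. Section 20.1 states: "All analyses will be done according to original patient allocation regardless of whether they received the randomized treatment". A rating of current treatment, compared by allocation, is a coherent treatment-policy comparison. Section 11.4 also leaves re-induction and return to Sublocade to the providers' discretion, so re-induction need not be a switch.
- **That improvement cannot be shown.** The section 7.2 objective compares the two drugs, and higher satisfaction on one than on the other can be shown from follow-up scores alone.

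The shorter wording in section 18.12, "How satisfied are you with your medication", is a description in a data table. It is not evidence of a second instrument.

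**Conclusion.** The point holds as a cheap improvement in precision, not as a flaw in validity. The plan omits a week 0 satisfaction score that every participant could give, at a time point where it already collects the WHOQOL-BREF. The model in section 20.12 therefore cannot adjust for prior satisfaction, and change from baseline cannot be described.

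The size is modest: a 9% to 25% cut in variance at a visit, and a detectable difference of 0.56 to 0.51 SD instead of 0.59 SD. This rests on r between 0.3 and 0.5, 45 per arm and complete data. The correlation could be weaker in the Sublocade arm, where the baseline and follow-up scores concern different drugs. If r were near zero, the gain would vanish.

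**What to change.** 1. In sections 12.21 and 13, add the MSQ item at week 0 alongside the WHOQOL-BREF, asked about Suboxone in both arms.
2. Require it before allocation is disclosed. The trial is open-label, so a later answer could be coloured by the assignment. Section 16.2 already holds back the randomization code until baseline screening measurements are complete, and the MSQ can join that set. The ±2-week questionnaire window in section 18.21 should not apply to this one score.
3. In section 20.12, name the week 0 score as a fixed covariate in the MSQ model, rather than leaving it to the clause on unbalanced baseline variables.
4. Keep the between-arm difference in follow-up scores as the outcome. Because the baseline rates Suboxone in both arms, a change score in the Sublocade arm would compare two different drugs. Change from baseline should be descriptive only.

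The cost is one spoken question at an existing visit, one form field and a sentence in the analysis section. It is of use only for participants not yet randomized when the change takes effect.
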